6.5 Secondary Efficacy Analyses

6.5.1 Hierarchical Testing

Primary inference for secondary efficacy endpoints will be based on analysis of the FAS analysis set using a repeated-measures linear mixed model for functional endpoints (see Section 6.5.2 below) and by Kaplan-Meier product-limit estimates and log-rank test for the primary survival endpoint (see Section 6.5.4 below). The sequence for testing secondary efficacy endpoints is the following:

1. HHD upper extremity percentage,
2. SVC,
3. HHD lower extremity percentage, and
4. Survival.

If the primary analysis indicates a significant slowing in disease progression from the Bayesian shared-parameter, repeated-measures model of ALSFRS-R and mortality, then each secondary efficacy endpoint in succession would be declared significant in the specified sequence using a comparison-wise criterion of two-tailed $p < 0.05$. After the first failure to declare significance, no endpoints lower in the hierarchy can be significant. This sequential closed-testing procedure controls the overall type 1 error rate at 5%. Nominal comparison-wise p-values for secondary efficacy endpoints will also be reported.

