6.5.2 Repeated-measures Model

The specification of the repeated-measures linear mixed model and the primary linear contrast for estimating differences in 24-week change from baseline in a given continuous efficacy endpoint (ALSFRS-R total and domain scores, HHD upper extremity, lower extremity, and global average percentages, SVC, FVC by home spirometry, serum creatinine, serum NfL, ALSAQ-40 domain scores and SI, and CNS-BFS total score) are revised from those specified in the M-SAP to include a main effect of treatment.

The model will include fixed terms for discrete visit, treatment group, treatment group \times visit interaction, centered time since symptom onset and centered time since symptom onset \times visit interaction, centered delta-FRS and centered delta-FRS \times visit interaction, centered baseline riluzole use and centered baseline riluzole \times visit interaction, and centered baseline edaravone use and centered baseline edaravone \times visit interaction. The following equations describe the model with regimen random effects:

$$Y_{ij} = a_{k(i)} + \gamma_1 t_i + \gamma_{2,j} v_j + \boldsymbol{\gamma}'_3 \mathbf{z}_i + \gamma_{4,j} t_i v_j + \boldsymbol{\gamma}'_5 \mathbf{z}_i v_j + \epsilon_{ij} \quad (\text{eqn. 1})$$

$$a_k \sim N(0, \sigma_r^2), \epsilon_i \sim N(\mathbf{0}, \mathbf{R}), \text{Cov}(b_{k(i)}, \epsilon_{ij}) = 0$$

where Y_{ij} is a given efficacy endpoint measured in participant i at visit j , $a_{k(i)}$ is a random intercept for regimen k to which participant i was assigned, v_j is an indicator variable for visit j , \mathbf{z}_i is the vector of covariates (centered time since onset, centered delta-FRS, centered baseline riluzole use, and centered baseline edaravone use) for participant i , t_i is an indicator variable for treatment t to which participant i was assigned, γ_1 , $\gamma_{2,j}$, $\boldsymbol{\gamma}_3$, $\gamma_{4,j}$, and $\boldsymbol{\gamma}_5$ are estimated parameters

and vectors of parameters for the fixed effects, and ϵ_{ij} is the residual for participant i at visit j . The regimen-specific random effects are normally distributed with mean 0 and variance σ^2_r . The vector of residuals for a given participant are normally distributed with mean $\mathbf{0}$ and an unstructured covariance matrix \mathbf{R} . The regimen-specific random effect for a given participant and residuals for that participant are uncorrelated.

The following SAS code specifies the model:

```

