proc mixed data=xxx method=reml;
  class regimen id trtrnd visit;
  model Value = trtrnd|visit
    sx2b1|visit dFRS|visit rlz|visit edv|visit / solution cl;
  random intercept / subject=regimen type=vc;
  repeated visit / subject=id type=un;
```

where `id` is a participant study identifier, `trtrnd` is the randomly assigned treatment group, `visit` is the visit identifier, `Value` is value of the efficacy endpoint being tested for a given participant at a given visit, `sx2b1` is years since ALS symptom onset centered at the sample median, `dFRS` is pre-baseline slope centered at the sample median, `rlz` is an indicator of riluzole use at baseline centered at the sample median, and `edv` is an indicator of edaravone use at baseline centered at the sample median. The primary estimate will be the treatment-dependent difference in change from baseline to the Week 24 Visit. The estimate and its 95% Wald confidence bounds will be obtained by a linear contrast of adjusted means. The following SAS code specifies the linear contrast for a regimen with one active treatment assuming an endpoint measured every 8 weeks and that the sort order for treatment group has the active group last and visits are sorted chronologically:

```
estimate "3|Act vs Plb|dWk 24" trtrnd*visit 1 0 0 -1 -1 0 0 1 / cl;
```

A significant difference in 24-week change from baseline in the direction of greater improvement or less worsening among participants randomized to active treatment would support inference of benefit from active treatment for the efficacy endpoint being tested. The estimand estimated by the primary linear contrast of the repeated-measures linear mixed model is the mean difference in 24-week change from baseline of a given continuous efficacy endpoint in the active treatment group relative to the placebo group in the FAS population. The estimand is defined by the following attributes:

- Treatment: zilucopan administered subcutaneously once daily at a dosage of approximately 0.3 mg/kg vs. placebo.
- Population: FAS population as defined in Section 6.1.
- Variables: absolute change in endpoint from baseline to the Week 24 Visit.
- Intercurrent event: treatment discontinuation: handled via treatment policy approach, all data will be used including data collected during the placebo-controlled period after treatment discontinuation. Missing data post-treatment, including data missing due to death, will not be imputed, handled via missing at random assumption.

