- Population-level summary: difference in conditional means of active treatment relative to placebo.

Inference from this analysis is supportive of inference from the Bayesian shared-parameter, repeated-measures model for the primary endpoint and is the primary analysis for secondary endpoints. A separate supportive analysis will include centered baseline serum NfL level and the interaction of centered baseline serum NfL level and visit as additional covariates.

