6.5.11 Comparison of Controls across Regimens

Comparisons of placebo participants across regimens are the same as specified in the M-SAP with separate analyses that include baseline serum NfL level as an additional covariate in adjusted analyses plus applicable interaction terms as relevant to a given model.

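### The repeated-measures model that decides HHD and SVC is valid, but it leaves pre-dose baseline serum NfL to a supportive fit; moving it into the governing model is a cheap, modest efficiency gain

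*SAP*

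**What the plan says.** SAP 6.5.1 sets the governing analysis: "Primary inference for secondary efficacy endpoints will be based on analysis of the FAS analysis set using a repeated-measures linear mixed model" for the functional endpoints. The order is HHD upper extremity, SVC, HHD lower extremity, then survival (by log-rank), each at two-sided 0.05. Testing opens only if the primary ALSFRS-R analysis succeeds and stops at the first failure. SAP 6.5.2 confirms that its model "is the primary analysis for secondary endpoints".

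The covariates of that model are the same in text, equation and code. The covariate vector is "centered time since onset, centered delta-FRS, centered baseline riluzole use, and centered baseline edaravone use", and the SAS model statement carries "sx2b1|visit dFRS|visit rlz|visit edv|visit / solution cl". NfL is in neither. It appears only at the end of 6.5.2: "A separate supportive analysis will include centered baseline serum NfL level and the interaction of centered baseline serum NfL level and visit" as further covariates.

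Elsewhere the SAP treats baseline serum NfL as an available adjustment variable:

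- 5.6 fixes the assay, the handling of values below quantitation and the log scale.
- 6.2 adds it to the baseline characteristics.
- 6.5.10 uses a median split of it as a subgroup in the FAS.
- 6.5.4 to 6.5.8 add NfL-adjusted versions of the survival, CAFS, HHD0, voice and imputation analyses.
- 6.5.11 plans "separate analyses that include baseline serum NfL level as an additional covariate in adjusted analyses" when placebo participants are compared across regimens, so NfL is expected in the shared placebos too.

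The schedules of activities in both documents put biomarker blood at Baseline, before dosing.

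**The concern.** A covariate measured before the first dose cannot be affected by treatment. If it predicts the outcome beyond the covariates already in the model, adjusting for it narrows the confidence interval at almost no cost. Here the sample is drawn, the assay is specified and the adjusted model is already to be programmed, yet the result that uses it has no standing in the hierarchy.

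Precision matters most for the first endpoint in the sequence. A narrow miss on HHD upper extremity also closes SVC, HHD lower extremity and survival. What is at stake is therefore some power in the secondary tests, not their validity. The primary ALSFRS-R analysis and the log-rank test of survival are outside this point.

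**Working it through.** **Is there a plan figure to reproduce?** No. The documents state no power, effect size or SD for HHD or SVC. Protocol 9.2 refers operating characteristics to simulation, and SAP 6.3 points to a separate design report. The effect of adding NfL therefore has to be shown over a range.

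**Inputs**
- Alpha: 0.05, two-sided (SAP 6.5.1).
- RGA allocation: 3:1 of about 160, that is 120 active and 40 placebo (Protocol, Regimen-Specific Appendix Summary).
- Shared placebos from regimens B, C and D: included in the FAS, number not given (SAP 6.1).
- r, the partial correlation of baseline log NfL with 24-week change, given the four existing covariates: not in the documents, **assumed** 0.2 to 0.4.
- Starting power: not in the documents, **assumed** 80%.

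**Step 1: standard error.** With complete data, the contrast of 24-week change has SE = σ × √(1/n_active + 1/n_placebo). Adding NfL and NfL × visit replaces σ by σ√(1 − r²). The SE ratio is therefore √(1 − r²) and the variance ratio is 1 − r².

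**Step 2: power.** From 80% power, the new power is Φ[(1.960 + 0.842)/√(1 − r²) − 1.960].

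| assumed r | variance falls by | SE ratio | SE falls by | power from an assumed 80% |
|---|---|---|---|---|
| 0.2 | 4% | 0.980 | 2.0% | 81.6% |
| 0.3 | 9% | 0.954 | 4.6% | 83.6% |
| 0.4 | 16% | 0.917 | 8.3% | 86.4% |

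**Step 3: dependence on shared placebos.** The sample-size term is common to both models and cancels. With 120 active against 40 placebo it is √(1/120 + 1/40) = 0.183; against an assumed 160 placebo it is √(1/120 + 1/160) = 0.121. The SE ratios in the table are the same in both cases.

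**Step 4: cost if NfL is uninformative.** At r = 0 one degree of freedom is lost for the contrast. With 160 participants the SE is multiplied by about √(153/152) = 1.003, a rise of 0.3%. It is smaller still in the larger FAS.

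**Step 5: simulation.** In 4,000 complete-data trials per value of r (120:40, least squares on change, four covariates against five), the mean SE ratios were 1.003, 0.983, 0.957 and 0.920 at r = 0, 0.2, 0.3 and 0.4. This agrees with Steps 1 and 4 once the lost degree of freedom is counted.

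**Step 6: missing NfL.** PROC MIXED drops records with a missing covariate. If a share m of participants lacks baseline NfL, the variance ratio becomes about (1 − r²)/(1 − m), and the model breaks even at r = √m: 0.14 at m = 2%, 0.22 at 5%, 0.32 at 10%. The documents give neither m nor, within this SAP, a rule for missing baseline NfL (3.6 refers to the M-SAP). Adding NfL without such a rule could lose precision.

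**The case against.** The strongest reply is that nothing is broken. The four-covariate model is prespecified and valid, the supportive role of NfL was a deliberate choice in SAP version 3.0, and the adjusted estimate will be reported anyway. All of that stands.

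The reply also says the loss is not shown. That stands too. No passage says how well NfL predicts HHD or SVC change once delta-FRS and time since onset are in the model by visit. The change log does speak of strong prognostic value, but about age in the survival models. A reader might infer that material power is certainly being lost; the documents do not support that.

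Two further inferences are tempting and should not be drawn:

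- **Bias from pooled controls.** RGA's permuted blocks do not balance RGA active against placebos from other regimens. But regimen assignment is itself random and stratified by the same riluzole and edaravone factors (SAP 2.5), only concurrently enrolling regimens contribute (6.1), and the within-RGA blocks do not stratify on NfL either (2.6). An NfL difference between active and pooled placebo is ordinary chance imbalance, which the standard error already covers.
- **A headcount.** Turning the variance gain into extra participants on a base of 160 describes RGA alone. The governing comparison is the FAS, whose placebo number is not stated. Only the relative gain carries over.

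The reply is also right that the M-SAP, which may explain the choice of covariates or handle missing ones, cannot be seen here, and that one model serves many endpoints, including serum NfL itself. These points limit the form of the change. They do not remove the case for it: the worst case is a fraction of a percent of the SE, provided no participant is dropped.

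**Conclusion.** The omission is confirmed in text, equation and code. It is a missed efficiency of uncertain size in a valid model. If r lies between 0.2 and 0.4, the SE of the HHD and SVC contrasts would be about 2% to 8% smaller, worth roughly 2 to 6 power points from an assumed 80%; if r is near 0, it would be about 0.3% larger. These figures rest on the assumed r, complete data, and a missing-NfL rule that keeps every FAS participant. The gain matters only if the primary analysis succeeds and the sequence opens. The change is worth making because it is cheap and its downside is small, not because the present tests are unsound.

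A separate documentary defect about NfL does need correction. SAP 6.5.3 lists NfL and NfL × month among the fixed terms of the main random-slopes model, but its covariate vector and SAS code omit them, and its closing paragraph makes the NfL version a separate supportive analysis. That model does not govern the confirmatory tests.

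**What to change.** Before data lock and unblinding:

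1. In SAP 6.5.1 and 6.5.2, make the model with centered log baseline serum NfL and NfL × visit the governing model for HHD upper extremity, SVC and HHD lower extremity only. Do not add the term when serum NfL is the endpoint.
2. Keep the present four-covariate model as the supportive fit for those three endpoints.
3. State a missing-covariate rule: set a missing baseline NfL to the FAS median and add a missing-value indicator and indicator × visit, so that PROC MIXED drops no FAS participant.
4. In SAP 6.5.3, make the text, covariate vector, code and closing paragraph agree on whether NfL belongs to the main random-slopes model.

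Cost: an amendment to a signed SAP whose version 3.0 already revised this model on FDA advice, so the swap should be documented with its reason. The NfL-adjusted code is already planned. For an endpoint with four visits, NfL and its interaction add four mean parameters, and the indicator four more if any value is missing. No new data are needed.

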6.5.3 Random-slopes Model

The specification of the random-slopes linear mixed model and the primary linear contrast for estimating differences in mean rate of progression in a given continuous efficacy endpoint (ALSFRS-R total and domain scores, HHD upper extremity, lower extremity, and global average percentages, SVC, FVC by home spirometry, quantitative voice characteristics, serum creatinine, serum NfL, ALSAQ-40 domain scores and SI, and CNS-BFS total score) are revised from those specified in the M-SAP to include a main effect of treatment and to specify that study months are calculated as the difference in days from the Baseline Visit to the date of assessment of a given endpoint multiplied by 12 / 365.25.

The model will include fixed terms for month since the Baseline Visit, treatment group, treatment group \times month interaction, centered years since ALS symptom onset and centered years since ALS symptom onset \times month interaction, centered delta-FRS and centered delta-FRS \times month interaction, centered baseline riluzole use and centered baseline riluzole use \times month interaction, centered baseline edaravone use and centered baseline edaravone use \times month interaction, and centered baseline serum NfL level and centered baseline serum NfL level \times month interaction. The following equations describe the model with regimen random effects:

$$\begin{aligned}
 Y_{ij} = & \gamma_1 + a_{k(i)}^0 + b_i^0 + \gamma_2 t_i + \boldsymbol{\gamma}_3' \mathbf{z}_i \\
 & + (\gamma_4 + a_{k(i)}^1 + b_i^1 + \gamma_5 t_i + \boldsymbol{\gamma}_6' \mathbf{z}_i) m_{ij} + \epsilon_{ij} \\
 \{a_k^0, a_k^1\} & \sim N(\mathbf{0}, \boldsymbol{\Sigma}_r), \{b_k^0, b_k^1\} \sim N(\mathbf{0}, \boldsymbol{\Sigma}_p), \epsilon_{ij} \sim N(0, \sigma_e^2) \\
 \text{Cov}(\mathbf{a}_k, \mathbf{b}_k) & = \mathbf{0}, \text{Cov}(\mathbf{a}_k, \boldsymbol{\epsilon}_{i.}) = \mathbf{0}, \text{ and } \text{Cov}(\mathbf{b}_k, \boldsymbol{\epsilon}_{i.}) = \mathbf{0}
 \end{aligned} \tag{eqn. 2}$$

where Y_{ij} is a given efficacy endpoint measured in participant i at visit j , $a_{k(i)}^0$ and $a_{k(i)}^1$ are random intercept and slope for regimen k to which participant i was assigned, b_i^0 and b_i^1 are random intercept and slope for participant i , \mathbf{z}_i is the vector of covariates (centered time since onset, centered delta-FRS, centered baseline riluzole use, and centered baseline edaravone use) for participant i , m_{ij} is the time from baseline to observation j for participant i in months calculated as days \times 12 / 365.25, t_i is an indicator variable for treatment t to which participant i was assigned, $\gamma_1, \gamma_2, \gamma_3, \gamma_4, \gamma_5$, and γ_6 are estimated parameters and vectors of parameters for the fixed effects, and ϵ_{ij} is the residual for observation j for participant i . The regimen-specific random effects are normally distributed with mean $\mathbf{0}$ and unstructured covariance matrix $\boldsymbol{\Sigma}_r$. The participant-specific random effects are normally distributed with mean $\mathbf{0}$ and unstructured covariance matrix $\boldsymbol{\Sigma}_p$. The residuals for a given participant are normally distributed with mean 0 and variance σ_e^2 . The regimen-specific random effects, participant-specific random effects, and residuals are uncorrelated.

The following SAS code specifies the model:

```

proc mixed data=xxx method=reml;
  class regimen id trtrnd;
  model Value = trtrnd|month
    sx2b1|month dFRS|month rlz|month edv|month / solution cl;
  
```

```
random intercept month / subject=regimen type=un;
random intercept month / subject=id type=un;
```

where month is time in months from the Baseline Visit (assuming 12 months in an average of 365.25 days per year) and other fields are the same as identified above in Section 6.5.2. The primary estimand will be the treatment-dependent difference in slopes. The estimate and its 95% Wald confidence bounds will be obtained by a linear contrast of adjusted means. The following SAS code specifies the linear contrast for a regimen with one active treatment assuming that the sort order for treatment group has the active group last:

```
estimate "3|Act vs Plb|Slope (/mn)" month 0 trtrnd*month -1 1 / cl;
```

A significant difference in slopes in the direction of greater improvement or less worsening among participants randomized to active treatment would support inference of benefit from active treatment for the efficacy endpoint being tested.

The estimand estimated by the primary linear contrast of the random-slopes linear mixed model is the difference in mean rate of progression of a given continuous efficacy endpoint in the active treatment group relative to the placebo group in the FAS population. The estimand is defined by the following attributes:

Treatment: zilucopan administered subcutaneously once daily at a dosage of approximately 0.3 mg/kg vs. placebo.

Population: FAS population as defined in Section 6.1.

Variables: mean rate of change in endpoint from baseline to the Week 24 Visit.

Intercurrent event: treatment discontinuation: handled via treatment policy approach, all data will be used including data collected during the placebo-controlled period after treatment discontinuation. Missing data post-treatment will not be imputed, handled via missing at random assumption.

Population-level summary: difference in conditional mean slopes of active treatment relative to placebo.

Inference from these analyses is supportive of inference from the Bayesian shared-parameter, repeated-measures model for the primary endpoint and inference from the repeated-measures linear mixed model for secondary endpoints. A separate supportive analysis will include centered baseline serum NfL level and the interaction of centered baseline serum NfL level and study month as additional covariates.

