6.5.10 Subgroup Analyses

In addition to the subgroups specified in the M-SAP, the following additional subgroups will be analyzed in the random-slope model (see Section 6.5.3) for primary and secondary efficacy endpoints in the FAS analysis set:

- Baseline use of riluzole and edaravone (neither, riluzole only, edaravone only, both),
- Age (less than 65 years vs. 65 years or older),
- Sex (female vs. male),
- Race (white vs. any minority race with greater than 5% prevalence in the sample),
- Ethnicity (Hispanic or Latino vs. non-Hispanic or Latino),
- Weight (less than 43 kg, 43 to less than 56 kg, 56 to less than 77 kg, 77 to less than 150 kg, 150 kg or more),
- BMI (less than 18.5 kg/m², 18.5 to less than 25 kg/m², 25 to less than 30 kg/m², 30 to less than 40 kg/m², 40 kg/m² or more),
- Chronic kidney disease (CKD) stage (stage 1 or better [eGFR 90 mL/min/1.73m² or more], stage 2 [eGFR 60 to 89 mL/min/1.73m²], stage 3 [eGFR 30 to 59 mL/min/1.73m²], stage 4 [eGFR 15 to 29 mL/min/1.73m²], stage 5 [eGFR less than 15 mL/min/1.73m²]),
- Time since onset of weakness (less than 18 months vs. 18 months or longer),
- El Escorial and time since onset of weakness (El Escorial definite and less than 18 months vs. not both),
- Baseline symptom severity (all ALSFRS-R questions scored 2 or greater vs. any question scored 0 or 1),
- Early disease state (all ALSFRS-R questions scored 2 or greater, SVC 80%-predicted or greater, and time since symptom onset less than 24 months vs. not meeting all three criteria),
- Baseline serum urate concentration (less than 5.5 mg/dL vs. 5.5 mg/dL or greater),
- Baseline serum NfL concentration (by median split), and
- Site (individual sites with at least 5 participants per treatment group and all participants from sites with fewer than 5 participants per treatment group pooled).

For each classification, unknown, not reported, and missing will be considered one group. All individuals not included in a specified subgroup will be combined into a mixed, "other" group. The "other" group will be included in analyses if its prevalence is greater than 5%; otherwise, the "other" group will be excluded.

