In cases where a model for a given subgroup and endpoint fails to converge, the covariance terms for the regimen-specific random effects will be simplified from unstructured covariance of intercepts and slopes to separate, uncorrelated variance components for intercepts and slopes. If convergence still fails, regimen-specific intercepts and slopes will be modeled as fixed effects. If convergence still fails, the participant-specific random effects will be simplified from unstructured covariance of intercepts and slopes to separate, uncorrelated variance components for intercepts and slopes.

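### The random-slopes code names no degrees-of-freedom method, so if the efficacy subgroups are fitted separately, their 95% bounds are too narrow in small levels

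*SAP*

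**What the plan says.** SAP section 6.5.3 prints the code that specifies the random-slopes model. It opens with "proc mixed data=xxx method=reml", and the MODEL statement ends "sx2b1|month dFRS|month rlz|month edv|month / solution cl". The random effects are "random intercept month / subject=regimen type=un" and "random intercept month / subject=id type=un". No degrees-of-freedom option appears in this code, and the SAP text names no such method. On the bounds it says "The estimate and its 95% Wald confidence bounds will be obtained by a linear contrast of adjusted means".

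Section 6.5.10 sends 15 additional subgroup classifications to this model, for the primary and secondary efficacy endpoints in the FAS. Site is one of them, defined by "individual sites with at least 5 participants per treatment group", with smaller sites pooled. Minority races and the residual category each need more than 5% prevalence. The weight, BMI and kidney-disease bands have no minimum size. The convergence rule begins "In cases where a model for a given subgroup and endpoint fails to converge". Its second step turns regimen intercepts and slopes into fixed effects.

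**The concern.** The treatment difference in slopes is a comparison between participants. Its precision depends mainly on how many participants there are and how much their slopes differ, and repeat visits on the same people add little to that. With RANDOM statements present and no option given, PROC MIXED applies the containment method. None of the listed random effects contains treatment by month, so the contrast receives residual degrees of freedom: observations minus the rank of the fixed and random design matrices together. With hundreds of participants the difference is trivial. With ten it is large.

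At stake is whether bounds labelled 95% for a small site, weight band or kidney-disease stage mean what they say. Section 6.5.3 treats a significant slope difference as support for benefit, so an interval that is too narrow could be read as a real local effect. Small sites are realistic: the protocol plans 120 active participants over about 60 centres, an average of 2 per centre, so sites that qualify will tend to lie near the floor.

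**Working it through.** **Reference figure.** The only figure the plan states is the nominal 95%, i.e. 5% two-sided error. It gives no variance components and no subgroup error rates.

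**Inputs**
- Visits T: ALSFRS-R has 7 (Weeks 0, 4, 8, 12, 16, 20, 24); SVC and HHD have 4 (Weeks 0, 8, 16, 24). Source: SAP 2.9.
- Slope parameters p as coded: intercept, treatment and four covariates, so p = 6. The text of 6.5.3 also lists baseline NfL, which the code omits; with it p = 7.
- Smallest site: 5 + 5, so n = 10 (SAP 6.5.10).
- FAS size: 160 randomised in this regimen plus an assumed 120 shared placebo, so n = 280. The documents give no shared-placebo count.

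**Closed form** (complete data, equal timing, no regimen effects, REML estimate not on the boundary):
- Containment df = nT − 2n, because the participant intercepts and slopes span the fixed effects.
- Between-participant df = n − p.
- Error = P(|t with n − p df| > 0.975 quantile of t with nT − 2n df).

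At 5 + 5 for ALSFRS-R, containment df = 70 − 20 = 50 and the critical value is 2.009. Between-participant df = 10 − 6 = 4 and the critical value should be 2.776. The interval is 1 − 2.009/2.776 = 28% too narrow and the error is 11.5%. For SVC and HHD, containment df = 40 − 20 = 20, the critical value is 2.086 and the error is 10.5%.

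| Setting | Between-participant df | ALSFRS-R error | SVC/HHD error |
|---|---|---|---|
| 5 + 5, as coded | 4 | 11.5% | 10.5% |
| 5 + 5, NfL added | 3 | 13.8% | 12.8% |
| 5 + 5, riluzole and edaravone not varying | 6 | 9.1% | 8.2% |
| 6 + 6 | 6 | 9.2% | – |
| 14 in total (5% of 280) | 8 | 8.1% | 7.5% |
| 8 + 8 | 10 | 7.5% | – |
| 10 + 10 | 14 | 6.7% | – |
| FAS, 280 | 274 | 5.1% | – |

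If Wald is read as a normal quantile, 5 + 5 as coded gives 12.2% for either endpoint, so the result does not hang on the SAS default.

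**Simulation at 5 + 5** (REML under the null, 2,000 datasets per setting, complete data, true regimen variance zero, containment df). The ratio is between-participant slope variance divided by that variance plus the sampling variance of one participant's fitted slope.

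| Model | Ratio 0.3 | Ratio 0.6 | Ratio 0.9 |
|---|---|---|---|
| No regimen effects, four covariates | 5.1–5.8% | 7.9–8.8% | 11.2–12.2% |
| Regimen random effects kept, four covariates | – | 12.6–13.3% | 23.5% |
| Regimen random effects kept, NfL added | – | – | 23.9% |
| Regimen as fixed effects | – | – | 20.5% |

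Ranges cover 4 and 7 visits; single figures at 0.9 are for 7. With regimen fixed and three regimen slopes estimable, n − p = 1, and the closed form gives 28–29%.

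**Does a between-participant df repair it?** Using n − p df without regimen effects, the error is 5.4–5.6% at ratio 0.9 and 1.5–3.4% (conservative) at 0.3 to 0.6. With regimen random effects kept and four covariates it is 5.4–6.0% at 0.6 but still 13.6% at 0.9. Kenward-Roger itself was not run.

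**The case against.** The strongest reply is that section 6.5.10 never states outright that each level gets its own model. It lists whole classifications, and the rule for including the residual category would also suit levels entered jointly. If subgroups are interaction terms in one FAS model, the error is about 5.1% and the problem disappears. This stands as a real ambiguity. The wording "In cases where a model for a given subgroup and endpoint fails to converge" points towards separate fits but does not settle the matter.

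The Master SAP, which was not supplied, might name a degrees-of-freedom method or a subgroup model. That also stands as a limit. However, 6.5.3 presents its code as the specification, revised from the Master SAP, and SAP section 1 gives the regimen SAP precedence over the Master SAP.

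Subgroups also lie outside the testing hierarchy of 6.5.1, 6.5.10 states no decision rule for them, and 6.5.3 calls random-slopes inference supportive. That limits the consequence but does not make the label of 95% correct.

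A reader might infer more than the documents support:
- **A fixed error rate, or one more than twice nominal across all 15 classifications.** The documents give no variance components. At 5 + 5 without regimen effects the rate is near 5% when slope variance is small. Even in the closed form it is below 10% from 6 + 6 upwards, and many classifications are broad two-way splits.
- **That every subgroup analysis is affected.** The adverse-event subgroups in 6.6.1 are summaries that do not use this model, and the Master SAP's own subgroups cannot be checked.
- **That the models in 6.5.2 and 6.5.7 share the fault.** No error was shown there.

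**Conclusion.** The point holds within limits. As printed, the 6.5.3 code gives the slope contrast degrees of freedom based on visits, and separate small fits under 6.5.10 would carry bounds that are too narrow. At a site on the 5-per-arm floor with four estimable covariates, the error is about 11.5% (10.5% for SVC and HHD) when between-participant slope variance dominates. Simulated rates at that size span about 5% to 24%, according to slope variance and regimen handling. The conclusion rests on separate fits per level, complete data, normal effects, and no overriding rule in the Master SAP. The weight, BMI and kidney-disease bands have no floor, so some could be smaller still or not estimable. The effect is confined to supportive subgroup estimates: the primary Bayesian analysis and the hierarchical tests do not use this contrast, and the full-FAS random-slopes result is essentially unchanged.

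**What to change.** 1. In 6.5.3, add `ddfm=kr` (Kenward-Roger) to the MODEL statement, and replace the reference to Wald bounds with bounds based on the resulting t quantile.
2. In 6.5.10, state that subgroup effects are estimated from one FAS model with subgroup × treatment × month terms and their lower-order terms, at least for small levels. This is needed as well as step 1, because a degrees-of-freedom correction alone may not fully repair separate small fits that keep regimen random effects. The size below which a level counts as small is for the team to choose and state.

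The cost is one SAS option and two or three sentences. Intervals in small subgroups will be wider, and the interaction model assumes common variances across levels.
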